4.2.6.2 Clinical Laboratory

All continuous laboratory parameters will be summarised descriptively by absolute value by each planned visit, together with the corresponding changes from baseline using the safety analysis set. These summaries will be produced for baseline and all scheduled post-baseline visits. All variables will be summarised in SI units.

Central laboratory normal reference ranges will be used for the identification of abnormalities. A shift table will be produced for each laboratory variable to display low, normal, and high values. The shift tables will present baseline and maximum/minimum post-baseline values for each variable.

In order to identify potential Hy's Law cases, maximum post-baseline TBL will be presented (<2 and $\geq 2 \times \text{ULN}$) against maximum post-baseline ALT (<3 , ≥ 3 - <5 , ≥ 5 - <10 , and $\geq 10 \times \text{ULN}$), expressed as multiples of ULN. This will be repeated to show maximum post-baseline TBL against maximum post-baseline AST. Maximum post-baseline TBL will also be plotted separately against both maximum post-baseline ALT and AST, expressed as multiples of ULN. These plots will be produced on a log scale, with reference lines included at $2 \times \text{ULN}$ for TBL, and at $3 \times \text{ULN}$ for both ALT and AST. These plots will be produced using all data for the on-study period.

For all subjects who meet the biochemical criteria for Hy's Law (potential Hy's Law cases), the relevant laboratory variables will be tabulated showing all visits for these subjects. Subjects with elevated ALT or AST in addition to elevated TBL at any time may be explored further graphically using individual subject profile plots.

A shift table will also be provided for each urinalysis qualitative assessment using the number and percentage of subjects with baseline results of negative or positive versus the maximum post-baseline result of negative or positive.

Any data outside the laboratory reference ranges will be flagged and explicitly noted on the listings that are produced.

A listing of all subjects tested for COVID-19 and including test results will be provided.

4.2.6.3 Vital Signs

All vital signs variables, including systolic blood pressure, diastolic blood pressure, pulse rate, weight, height, body mass index (BMI), respiratory rate and body temperature, will be summarized by absolute value at each visit using the safety analysis set, together with the corresponding changes from baseline. These summaries will be produced for baseline and all scheduled post-baseline visits.

The normal reference ranges listed in [Table 2](#) will be used for the identification of individual abnormalities. A shift table will be produced for each vital sign variable (Diastolic Blood Pressure, Systolic Blood Pressure, Pulse Rate, Respiratory Rate, Body Temperature) to display low, normal, and high values. The shift tables will present baseline and maximum/minimum post-baseline values for each variable. Additionally, the incidence of clinically notable vital signs abnormalities, as judged by the investigator, will be summarised.

All recorded vital signs data will be listed.

[figure not shown]

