8.2.2 Vital Signs

Vital signs will be performed at timelines as specified in the SoA ([Table 1](#)). If required, this may be done by a study nurse at the subject's home on the Day 11 visit, if previously approved and agreed with AstraZeneca.

Vital signs (blood pressure [BP], heart rate, respiratory rate and body temperature) will be obtained in accordance with SoA.

On Day 1, vital signs will be assessed within 1 hour prior to and at 1 hour and 2 hours post-IP administration.

Vital signs will be taken prior to blood drawing, and, if possible, usual asthma controller medication.

Blood pressure and pulse measurements will be assessed in sitting position with a completely automated device. Manual techniques will be used only if an automated device is not available.

Blood pressure and pulse measurements should be preceded by at least 5 minutes of rest for the subject in a quiet setting without distractions (eg, television, cell phones).

Pulse rate will be obtained before BP, if the manual measurement technique is used.

Respiration rate will be obtained after the subject has been resting for at least 5 minutes, by counting number of breaths (ie, how many times the chest rises) for one minute.

Body temperature will be measured prior to IP administration, in accordance with local standards.

See Section [8.3.5](#) for reporting AEs based on vital signs.

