Important protocol deviations will be defined at subject level prior to DBL and will be summarised and listed. The definitions of each category of important protocol deviation will be fully specified in the study Non-Compliance Handling Plan and will include (but may not be limited to): subjects who received IP without fulfilling key entry criteria; subjects who received prohibited or restricted concomitant medications during the study; subjects who received the incorrect IP dose.

In general, the last valid non-missing measurement taken on or prior to the date of treatment will serve as the baseline measurement. If there is no value on or prior to the date of treatment, then the baseline value will not be imputed and will be set to missing.

Absolute change from baseline is defined as the difference between the relevant post-baseline value and the baseline value. Unless specified otherwise, “change from baseline” is assumed to be absolute change from baseline.

Further details regarding baseline and/or change from baseline definitions will be provided in the SAP.

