3 PRIMARY AND SECONDARY VARIABLES

3.1 General Principles

3.1.1 Baseline Definitions

Baseline is defined as the last valid non-missing result obtained on or prior to the date of dosing of tezepelumab.

If there is no result prior to dosing of tezepelumab, then the baseline value will not be imputed and will be set to missing.

Absolute change from baseline is defined as the difference between the relevant post-baseline value and the baseline value. If either the post-baseline value or the baseline value is missing, then the absolute change from baseline will also be missing.

Unless specified otherwise, "change from baseline" is assumed to be the absolute change from baseline.

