3.1.4 Visit Windows

Summaries and analyses for which data are presented by study day (e.g. “Day 1”) will use the analysis visit windows to classify the data record, which is derived from the assessment date relative to the date of IP administration. Study Day is defined as specified in Section 3.1.2, unless specified otherwise.

Visit window is allowed only for the visits specified in Table 1.

Table 1 Visit windows allowed

Visit	Target Day	Visit Window
V4	Day 7	4-8
V5	Day 11	9-12
V6	Day 15	13-21
V7	Day 29	22-42
V8	Day 57	43-70
V9	Day 85	71-88

Nominal database visit numbers will not be used in any summary or analysis by visit.

Any data collected at unscheduled or repeat visits will be listed and will be included in baseline definitions (see Section 3.1.1), and in any definitions of maximum value, minimum value or last value within the relevant study period.

Measurements collected from unscheduled visits, repeat assessments or early study discontinuation visits may also be considered in the analysis visit window. In the case of a missing value at a scheduled visit, which is then followed by a non-missing value at an unscheduled or repeat assessment within the same visit window, the non-missing value at the unscheduled/repeat assessment will be used.

If a subject has more than one non-missing value within the same visit window, the following rules will apply:

- The non-missing value closest to the target day will be selected for analysis at that visit,
- If two non-missing values are the same distance from the target day, the earlier of the two values will be selected for analysis at that visit,
- If two non-missing values are recorded on the same day and have a different assessment time associated with both of them, the value with the earliest assessment time will be selected for analysis at that visit,
- If two non-missing values (for continuous variables) are recorded on the same day and have no assessment time associated with at least one of them, or the same assessment time associated with both of them, the average of the two values will be selected for analysis at that visit. For categorical variables in this situation, the worst case will be used.

If a subject has no value within a particular visit window, then the subject will have a missing value on that CSP scheduled study day in summaries and analysis.

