3.4.3 Vital Signs

Vital signs (systolic blood pressure, diastolic blood pressure, pulse rate, weight, height, Body mass index (BMI), respiratory rate and body temperature) will be assessed.

Vital sign results will be compared to the given reference ranges ([Table 2](#)) and classified as low (below range), normal (within range or on limits) or high (above range). All results falling outside the reference ranges will be flagged in the listings. The investigator will assess the results with regards to clinically relevant abnormalities. In addition, changes in vital signs between baseline and each subsequent scheduled assessment will be calculated.

Table 2 Vital Signs Reference Ranges for Age 5-11 Years

[figure not shown]
Parameter	Standard Units	Lower Limit	Upper Limit
Diastolic Blood Pressure	mmHg	57	80
Systolic Blood Pressure	mmHg	97	120
Pulse Rate	bpm	70	110
Respiratory Rate	breaths/min	20	30
Body Temperature	°C	35.5	37.5
Weight	kg	15	NA

3.4.4 **Electrocardiograms**

[figure not shown]
A 12-lead ECG will be performed at timelines as specified in Table 1 of the CSP, using local site equipment after at least 5 minutes of rest for the subject in a quiet setting without distractions.

The outcome of the investigator's overall ECG evaluation will be recorded as normal/abnormal in the CRF and with any abnormalities recorded as not clinically significant or clinically significant.

CCI

CCI

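### Baseline is bounded by the dosing date, so read literally the 2 h post-injection vital signs become baseline, and the 1 h and 2 h readings have no summary row

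*SAP*

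**What the plan says.** Protocol 8.2.2 sets the schedule: "On Day 1, vital signs will be assessed within 1 hour prior to and at 1 hour and 2 hours post-IP administration". Footnote c of the Schedule of Activities gives the same three times. Follow-up vital signs are then taken at V3 to V9 (Days 3, 7, 11, 15, 29, 57 and 85).

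Four parts of the SAP bear on these readings:

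- **Derivation.** SAP 3.4.3 states that "changes in vital signs between baseline and each subsequent scheduled assessment will be calculated".
- **Display.** SAP 4.2.6.3 gives summaries of level by visit, "together with the corresponding changes from baseline. These summaries will be produced for baseline and all scheduled post-baseline visits".
- **Baseline.** SAP 3.1.1 reads: "Baseline is defined as the last valid non-missing result obtained on or prior to the date of dosing of tezepelumab". Its next sentence, on missing baselines, begins "If there is no result prior to dosing of tezepelumab".
- **Windows.** SAP 3.1.4 says "Visit window is allowed only for the visits specified in Table 1", and that table runs from V4 to V9.

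Protocol 9.4.1 has the same date bound, "the last valid non-missing measurement taken on or prior to the date of treatment will serve as the baseline measurement", and adds: "Further details regarding baseline and/or change from baseline definitions will be provided in the SAP".

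**The concern.** There are two linked problems. First, the 1 h and 2 h readings are scheduled assessments but not visits. The SAP derives their changes from baseline but names no row in which to show them. Second, a baseline bounded by date cannot separate three readings taken on the same day. Under the rule as written, the last of them, taken 2 h after the injection, is the baseline.

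Protocol 2.3.1 names vital-sign monitoring for at least 2 h after dosing as a risk-mitigation measure and lists serious hypersensitivity as a potential risk. Vital signs are a stated safety outcome. A summary of level and change over those 2 h is what these readings could supply and what the plan leaves out. On the literal baseline, later changes also start from a value that may already reflect the injection, and the 1 h reading drops out of the shift tables.

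**Working it through.** The plan gives no figure of its own to reproduce. The check applies its rules to the planned schedule.

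**Inputs**
- Day 1 readings: pre-dose, 1 h and 2 h (Protocol 8.2.2).
- Follow-up sets: 7, at V3 to V9 (Protocol Table 1).
- Children dosed: about 14 (SAP 1.3).
- Variables: systolic and diastolic pressure, pulse, respiratory rate and temperature, so 5. Footnote c includes temperature after dosing, but Protocol 8.2.2 also says temperature is measured before dosing. The count is therefore 4 if it is not taken afterwards.
- Systolic reference range: 97 to 120 mmHg (SAP Table 2).

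**Readings without a row**
- Post-dose sets per child: 2 + 7 = 9.
- Sets with no specified row: 2, and 2/9 = 22%.
- In 14 children: 2 × 14 = 28 sets.
- Values: 28 × 5 = 140, or 28 × 4 = 112 without temperature.

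**Which reading is baseline under each rule**

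| Rule | Baseline | Post-baseline sets |
|---|---|---|
| SAP 3.1.1 read literally (date only) | Day 1, 2 h | 9 - 2 = 7 (Days 3 to 85) |
| Last value before the injection time | Day 1, pre-dose | 9 (1 h, 2 h, Days 3 to 85) |

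Under the first rule the 1 h reading is neither baseline nor post-baseline. Later changes measured from a post-injection value number 7 × 14 = 98 per variable.

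**Effect on later changes**

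(later - 2 h) = (later - pre-dose) - (2 h - pre-dose)

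With d = 2 h - pre-dose, each later change moves by -d.

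**Hypothetical child**, systolic pressure 108 pre-dose, 96 at 1 h, 100 at 2 h, and 108 from Day 3 to Day 85:
- Pre-dose baseline: 96 - 108 = -12; 100 - 108 = -8; then 108 - 108 = 0. The lowest post-baseline value is 96, below 97, so the shift is normal to low.
- Literal baseline of 100: 108 - 100 = +8 at all 7 visits. The lowest post-baseline value is 108, so the shift is normal to normal.

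The child shows the direction of the error. It does not estimate how often the error would occur.

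**The case against.** The strongest reply is that nobody would program the literal rule. The second sentence of SAP 3.1.1 makes best sense if baseline is pre-dose. SAP 3.4.3 wants a change at every subsequent assessment, which the 1 h reading could not have if the 2 h value were baseline. Protocol 8.3.11 treats the vital signs before dosing as the pre-assessment. SAP 3.1.4 keeps the earliest of two timed values on the same day, which would favour the pre-dose reading.

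These texts show the likely intent, but they do not replace the stated rule. The second sentence of 3.1.1 governs only missing baselines. The earliest-time rule selects values within visit windows, Day 1 has no window, and it is not a baseline rule. Stretched to Day 1, it would drop the 1 h and 2 h readings and still give them no row.

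The second reply is that rows within a visit are usually settled in table shells, which are not among the documents, and that the visit-level wording matches Protocol 9.4.3. Both points are correct: this is not a departure from the protocol, and an unstated row is not an excluded one.

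The third is that the information appears elsewhere, and this limits the weight of the point. All readings are listed and out-of-range values flagged. Investigator-judged notable abnormalities are summarised, and clinically relevant deteriorations are reported as AEs (Protocol 8.3.5). Anaphylactic and injection site reactions are AESIs, and SAP Appendix B ties potential anaphylaxis to the timing of the injection. With a pre-dose baseline, both readings also enter the shift tables. Those tables pool extremes up to Day 85, however, and do not show timing, and listings do not summarise change.

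**Conclusion.** The concern holds, as a minor point. The baseline rule in SAP 3.1.1 is wrong as written for vital signs: applied literally, it selects a post-injection value, reduces the post-baseline sets from 9 to 7, and moves every later change by -d. Separately, 2 of 9 post-dose sets per child have no specified summary row.

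The counts assume about 14 dosed children with complete readings. The damage from the baseline rule also assumes that it is programmed as written, which the rest of the SAP suggests was not intended. No SD or expected size of d is given or assumed. A mean change in a single arm cannot be attributed to the drug, marked individual events would still be seen, and no PK endpoint is affected.

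**What to change.** Make three changes to the SAP:

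1. **3.1.1:** for vital signs, define baseline as the last valid non-missing value recorded before the time of injection.
2. **3.1.4:** state that Day 1 pre-dose, 1 h and 2 h are separate analysis time points.
3. **4.2.6.3:** add Day 1 1 h and 2 h rows for systolic and diastolic pressure, pulse, respiratory rate and (where measured) temperature, showing level and change from the pre-dose value, as description only.

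The cost is three sentences and two extra rows in each of five tables. The readings are already scheduled and the injection time is already recorded in the eCRF (Protocol 6.4), so the children face no further procedures.

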4.2.6.4 Electrocardiograms

The outcome of the overall investigator ECG evaluation recorded as normal or abnormal with any abnormalities recorded as not clinically significant or clinically significant will be listed for all subjects by safety analysis set.

Abnormal values will not be recorded as AEs unless deemed clinically significant.

A summary table will be produced for ECG evaluations at baseline and all scheduled post-baseline visits to display normal, abnormal – not clinically significant, abnormal – clinically significant and not done.

CCI

5 INTERIM ANALYSES

No formal interim analyses are planned in this trial.

6 CHANGES OF ANALYSIS FROM PROTOCOL

In the change to the protocol, Day 29 PK analysis results will be evaluated to confirm the dose of Tezepelumab selected for the future safety and efficacy study in 5 to <12 years old children.

8 APPENDIX

Appendix A Handling Incomplete Dates for Adverse Events and Medications

Dates missing the day or both the day and month of the year will adhere to the following conventions in order to classify on-study AEs and to classify prior and concomitant medications.

In general, listings will present the actual partial or missing values rather than the imputed values that may be used in derivation. In instances where imputed values will be presented, impute values will be flagged.

Adverse Events

- The missing day of onset of an AE will be set to:
 - First day of the month that the event occurred, if the onset YYYY-MM is after the YYYY-MM of IP dosing
 - The day of IP dosing, if the onset YYYY-MM is the same as YYYY-MM of IP dosing
 - The date of informed consent, if the onset YYYY-MM is before the YYYY-MM of IP dosing.
- The missing day of resolution of an AE will be set to:
 - The last day of the month of the occurrence. If the subject died in the same month, then set the imputed date as the death date.
- If the onset date of an AE is missing both the day and month, the onset date will be set to:
 - January 1 of the year of onset, if the onset year is after the year of IP dosing.
 - The date of IP dosing, if the onset year is the same as the year of IP dosing.
 - The date of informed consent, if the onset year is before the year of IP dosing.
- If the resolution date of an AE is missing both the day and month, the date will be set to:
 - December 31 of the year of occurrence. If the subject died in the same year, then set the imputed date as the death date.

Prior/concomitant medication

Dates missing the day or both the day and month of the year will adhere to the following conventions in order to classify prior/concomitant medications:

- The missing day of start date of a therapy will be set to the first day of the month of the occurrence.
- The missing day of end date of a therapy will be set to the last day of the month of the occurrence.

- If the start date of a therapy is missing both the day and month, the onset date will be set to January 1 of the year of occurrence.
- If the end date of a therapy is missing both the day and month, the date will be set to December 31 of the year of occurrence.
- If the start date of a therapy is null and the end date is not a complete date, then the start date will be set to the date of the first study visit.
- If the start date of a therapy is null and the end date is a complete date:
 - and the end date is after the date of the first study visit then the start date will be set to the date of the first study visit.
 - otherwise the start date will be set to the end date of the therapy.
- If the end date of a therapy is null and the start date is not a complete date, then the end date will be set to the date of the last study visit.
- If the end date of a therapy is null and the start date is a complete date:
 - and the start date is prior to the date of the last study visit then the end date will be set to the date of the last study visit.
 - otherwise, the end date will be set to the start date of the therapy.

Appendix B Preferred Terms for Adverse Events of Special Interest

Anaphylactic reactions

Potential anaphylactic reactions will be defined on the basis of Sampson's criteria (see Sampson et al., 2006). These will be identified using a modified Standardized MedDRA Query (SMQ), with additional constraints on the timing of the AE onset date relative to the timing of the injection.

Confirmed anaphylactic reactions will be those defined following medical review of the preferred terms identified as potential anaphylactic reactions, as well as any relevant supporting data.

AESIs and related definitions based on MedDRA terms are not included in this SAP to facilitate their maintenance (e.g. management of MedDRA version changes), and for convenience in using them directly in SAS programming. These detailed definitions will be finalised by the study team prior to the primary database lock and provided together with the study datasets at the time of submission.

Immune complex disease (Type III hypersensitivity reactions)

Immune complex disease will be defined using a single PT of "Type III immune complex mediated reaction". Since this will already be covered by the general AE reporting by SOC/PT, separate summary tables will not be needed for this AESI.

Malignancy

Malignancy will be defined on the basis of an SMQ.

AESIs and related definitions based on MedDRA terms are not included in this SAP to facilitate their maintenance (e.g. management of MedDRA version changes), and for convenience in using them directly in SAS programming. These detailed definitions will be finalised by the study team prior to the primary database lock and provided together with the study datasets at the time of submission.

Helminth infections

Helminth infection will use an investigator-driven definition, i.e. will be directly determined from what is entered on the eCRF.

A subject will be considered to have this AESI if the subject has at least one preferred term where the dedicated Helminth Infection eCRF page was also completed for that event (linked by AE number), with AE onset date during the relevant study period for analysis.

Severe infections (as defined in the protocol)

Severe infections will use an investigator-driven definition, i.e. will be directly determined from what is entered on the eCRF.

A subject will be considered to have this AESI if the subject has at least one preferred term with AE onset date during the relevant study period for analysis, which satisfies the following:

- “AE Category” on Adverse Events eCRF page marked as “Severe Infection”, and one or more of the following:
 - AE is serious (“Serious” on Adverse Events eCRF page marked as “Yes”), or
 - AE required treatment with systemic antiviral medications, intravenous antibiotics or medications for Helminth parasitic infection.

Injection site reactions

Injection site reactions will use an investigator-driven definition, i.e. will be directly determined from what is entered on the eCRF.

A subject will be considered to have this AESI if the subject has at least one preferred term with AE onset date during the relevant study period for analysis, which has “AE category” on the Adverse Events eCRF page marked as “Injection Site Reaction”.

Opportunistic infections

Opportunistic infections will be defined using a pre-specified list of preferred terms (AZ defined SMQ).

AESIs and related definitions based on MedDRA terms are not included in this SAP to facilitate their maintenance (e.g. management of MedDRA version changes), and for convenience in using them directly in SAS programming. These detailed definitions will be finalised by the study team prior to the primary database lock and provided together with the study datasets at the time of submission.

Guillain-Barre syndrome

Guillain-Barre syndrome will be defined using an SMQ.

AESIs and related definitions based on MedDRA terms are not included in this SAP to facilitate their maintenance (e.g. management of MedDRA version changes), and for convenience in using them directly in SAS programming. These detailed definitions will be finalised by the study team prior to the primary database lock and provided together with the study datasets at the time of submission.

SIGNATURE PAGE

This is a representation of an electronic record that was signed electronically and this page is the manifestation of the electronic signature

Document Name: d5180c00025-SAP-v2.0		
Document Title:	d5180c00025 Statistical Analysis Plan v2.0	
Document ID:	CCI [REDACTED]	
Version Label:	2.0 CURRENT LATEST APPROVED	
Server Date (dd-MMM-yyyy HH:mm 'UTC'Z)	Signed by	Meaning of Signature
02-Aug-2022 09:13 UTC	PPD [REDACTED]	Content Approval
02-Aug-2022 11:45 UTC	PPD [REDACTED]	Content Approval
02-Aug-2022 09:27 UTC	PPD [REDACTED]	Author Approval

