8.3.4 Adverse Events Based on Signs and Symptoms

All AEs spontaneously reported by the subject or care provider or reported in response to the open question from the study-site staff: ‘Have you/the child had any health problems since the previous visit/you were last asked?’ or revealed by observation will be collected and recorded in the eCRF. When collecting AEs, the recording of diagnoses is preferred (when possible) to recording a list of signs and symptoms. However, if a diagnosis is known and there are other signs or symptoms that are not generally part of the diagnosis, the diagnosis and each sign or symptom will be recorded separately.

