8.3.7 Adverse Events of Special Interest

An AE of special interest (AESI) is an event of scientific and medical interest towards improving the understanding of the IP. An AESI may be serious or non-serious. For this study, AESIs include:

- Anaphylactic reactions
- Immune complex disease (Type III hypersensitivity reactions)
- Malignancy
- Helminth infections
- Severe infections which are defined as:
 - SAEs or
 - Requiring treatment with systemic antiviral medications, intravenous antibiotics or medications for helminth parasitic infection.
- Injection site reactions
- Opportunistic infections
- Guillain Barre Syndrome.

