9.4.3 Safety

Safety analyses will be performed using the safety analysis set. Safety data will be presented using descriptive statistics unless otherwise specified.

Verbatim terms of AEs will be coded to a standardised PT using the MedDRA version in force at DBL.

The overall number and percentage of subjects with AEs and SAEs will be presented. The occurrence of AEs and SAEs will be described also by SOC, PT and separately by severity and by relationship to the IP (as determined by the Investigator). Should a subject report the same PT/SOC within multiple severity or relationship categories, the subject's worst occurrence (most severe/most related) will be tabulated.

Serious AEs, AEs leading to death, AEs leading to withdrawal from study, commonly occurring AEs and AESIs will be summarised by SOC and PT.

Laboratory data, including serum chemistry, haematology and urinalysis will be summarised by presenting summary statistics of observed and change from baseline values at each scheduled assessment visit. Shift tables using normal ranges (baseline to most extreme postbaseline value) will also be presented. The incidence of clinically notable laboratory abnormalities will be summarised. Shift tables will also be provided.

Number of subjects with elevated liver function tests that meet the HL definition will be summarised and evaluated.

Vital signs data will be summarised by presenting summary statistics of observed and change from baseline values at each scheduled assessment visit. The incidence of clinically notable vital signs abnormalities will be summarised.

Abnormal ECGs as per Investigator's overall interpretation will be summarised using frequency and percentage of subjects.

Additional analyses assessing the impact of COVID-19 may be included in the SAP.

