4.2.6.1 Adverse Events

All AEs experienced by the subjects will be collected throughout the study, as per CSP Table 1, and will be coded by IQVIA using the latest version of MedDRA at the time of database lock.

Adverse events and SAEs will be categorised for analysis according to their onset date into occurring during the screening period or the on-study period. Adverse events occurring during the screening period will only be presented in the subject listing. Adverse events occurring during the on-study period will be summarised and listed as follows:

An overall summary table will be produced showing the number and percentage of subjects with at least one AE in each of the following categories: any AEs, SAEs, AEs with outcome of death, and AEs leading to withdrawal from study. The total number of AEs in the different AE categories in terms of AE counts will also be presented (i.e. accounting for multiple occurrences of the same event in a subject).

Adverse events, SAEs, AEs with outcome of death, AESIs and AEs leading to withdrawal from study will be summarised by SOC and PT assigned to the event using the MedDRA dictionary by descending frequency order. For each PT, the number and percentage of subjects reporting at least one occurrence of the event will be presented (i.e. subjects with multiple occurrences of the same PT will only be counted once).

Adverse events and SAEs will be summarized by PT and Investigator's causality assessment (related versus not related) and maximum intensity. If a subject reports multiple occurrence of the same AE within the same reported period, the maximum intensity will be taken as the highest recorded maximum intensity (the order being severe, moderate, and mild).

Separate listings of subjects with AEs, SAEs, AEs with outcome of death and AEs leading to withdrawal from study will be presented.

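### One preferred term stands in for a whole class of Type III reactions, so a case coded to any other term would not be flagged as this AESI

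*SAP*

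**What the plan says.** Protocol 8.3.7 lists eight AESIs. One is immune complex disease, which it explains in brackets as Type III hypersensitivity reactions. That names a class, not a coded term.

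SAP Appendix B makes it operational: "Immune complex disease will be defined using a single PT of" Type III immune complex mediated reaction. It then says: "Since this will already be covered by the general AE reporting by SOC/PT, separate summary tables will not be needed for this AESI".

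Two rules in the protocol decide what reaches that definition. Section 8.3.4 says that "the recording of diagnoses is preferred (when possible) to recording a list of signs and symptoms". Section 9.4.3 says that "Verbatim terms of AEs will be coded to a standardised PT using the MedDRA version in force at DBL".

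On reporting, Protocol 9.4.3 says that "commonly occurring AEs and AESIs will be summarised by SOC and PT", and SAP 4.2.6.1 says that "AESIs and AEs leading to withdrawal from study will be summarised by SOC and PT". Neither makes an exception for immune complex disease.

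**The concern.** The protocol asks for a class of reactions and the SAP counts one PT. The two agree only if every Type III reaction in the study is coded to that PT. The term is named for the immunological mechanism, while sites are steered towards the diagnosis. A reaction recorded under a diagnosis with its own PT, or only as signs and symptoms, would fall outside the definition, and nothing in Appendix B would bring it back.

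The AESI matters here because immunogenicity is the only secondary objective. Protocol 8.5.2.1 calls for an extra anti-drug antibody (ADA) sample when an immunologically related event is suspected. Protocol 9.4.2.2 and SAP 4.2.5.2 leave room to look at ADA against safety. Immune complex disease is directly relevant to that question. The study also precedes safety and efficacy studies in the same age group (Protocol 2.1), so its AESI summary is likely to be read by those planning them.

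**Working it through.** The plan gives no expected AESI rate and no formal sample size calculation (Protocol 9.2), so there is no figure of its own to reproduce. The check is a comparison of definitions, a trace of how an event is classified, and a short illustration.

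**Definitions in SAP Appendix B**

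| AESI | How it is identified |
|---|---|
| Anaphylactic reactions | Modified SMQ with timing limits, then medical review |
| Malignancy | SMQ |
| Opportunistic infections | Pre-specified term list (sponsor-defined SMQ) |
| Guillain-Barre syndrome | SMQ |
| Helminth infections | Investigator entry on a dedicated eCRF page |
| Severe infections | Investigator-marked eCRF category plus criteria |
| Injection site reactions | Investigator-marked eCRF category |
| Immune complex disease | One PT |

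Four use an SMQ or list, three use the eCRF, and one uses a single PT: 4 + 3 + 1 = 8. For the four SMQ or list AESIs, Appendix B also commits to finalising detailed definitions before the primary database lock. That commitment is absent under immune complex disease.

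**Trace of one event**

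1. A Type III reaction occurs and the site records it, as a diagnosis if possible (Protocol 8.3.4).
2. The verbatim term is coded to a PT (Protocol 9.4.3).
3. If the PT is the one named in Appendix B, the event is this AESI.
4. If it is any other PT, the event is not this AESI. No term list, eCRF category or review step applies.
5. Either way it enters the all-event SOC/PT table, the PT tables by causality and intensity, and the subject listings (SAP 4.2.6.1). That section plans no AESI row in its overall table and no separate AESI listing, so nothing there groups the cases.

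**Illustration**

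Inputs: n = 14 treated (approximate) and 12 completing (minimum aimed for), both from Protocol 9.2. Assumption: k Type III reactions, each in a different child and each coded to a PT other than the listed one.

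- Single-PT rule: 0/14 = 0.0% for any such k.
- Definition that captures them, k = 1: 1/14 = 7.1%.
- Same, k = 2: 2/14 = 14.3%.
- Same, k = 1 with n = 12: 1/12 = 8.3%.

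For scale, suppose capture is complete and the count is 0/14. The exact upper bound on the true rate is then 1 − 0.05^(1/14) = 19.3% (one-sided 95%), or 1 − 0.025^(1/14) = 23.2% (upper end of a two-sided 95% interval). With so few children, a single case carries much of the information.

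**The case against.** The case for leaving the text alone has several parts.

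- **The coding step cannot be verified.** Neither document reproduces MedDRA. A reader might infer that typical clinical diagnoses all code elsewhere and that capture of them is nil. The documents do not show this. They support only that a one-term definition may not cover the named class. This stands.
- **Sites can use the AESI's own wording.** Protocol 8.3.7 puts the name in front of them, and 8.3.4 states a preference for diagnoses that does not prevent its use. This stands: some cases may well reach the listed PT.
- **No AESI-specific zero is planned.** A reader might infer that the report will state the AESI to be absent. Appendix B plans no separate table, so the visible effect would be a missing PT row in the general table. The event stays in the tables and listings, and with about 14 children a reviewer can read every line. This stands and limits the harm to a missing flag.
- **The waiver need not contradict SAP 4.2.6.1.** If one PT is the whole AESI, the general SOC/PT table already summarises it. This stands as far as it goes: the conflict with SAP 4.2.6.1 and Protocol 9.4.3 arises only if one PT does not cover the class.
- **The list may change.** SAP 3.4.1 allows the AESI terms to be updated as safety data accumulate. That is permission, not a commitment, and Appendix B states a closed definition for this AESI. It does not remove the point.
- **This is not the first paediatric exposure.** A reader might rank this AESI higher on that ground. Protocol 2.2 describes earlier dosing of adolescents aged 12 to 17, and no section ranks this AESI above the other seven.

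**Conclusion.** The point holds as a modest, inexpensive improvement to the safety analysis. A stated rule, not a missing detail, defines a class of reactions by one PT. It gives this AESI none of the tools that each of the other seven has in some form. A Type III reaction coded to another PT would be misclassified, though not lost.

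The size is conditional. One such case among about 14 treated children gives 0/14 instead of 1/14 (7.1%). This assumes that such a case occurs and that its recorded diagnosis or signs code to a different PT. The documents give neither a probability for the first nor a coding map for the second. No claim is made about which diagnoses would be missed or what share of cases they form.

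**What to change.** Before database lock, change SAP Appendix B in three places.

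1. Define immune complex disease by a pre-specified PT list or SMQ that includes the current PT. The sponsor's coding team should check the candidate terms against the MedDRA version in force. Add the commitment, already made for the four SMQ or list AESIs, to finalise the definition before the primary database lock.
2. Follow the term search with medical review, as Appendix B already does for anaphylaxis, so that candidate events are confirmed or set aside with a reason.
3. Remove the statement that "separate summary tables will not be needed for this AESI". Its rationale holds only for a single PT. Summarise this AESI by SOC and PT, as SAP 4.2.6.1 and Protocol 9.4.3 already provide.

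The cost is a short term list in the external AESI file, a small edit to Appendix B and medical review of a few candidate events in about 14 children. One drawback is that the definition may then differ from a single-PT definition, if one is used elsewhere. Reporting the single-PT count beside the broader one would keep that comparison available.
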